### **8.6.3 Summaries of Baseline Characteristics, Demographics, and Other Analyses**

#### **8.6.3.1 Demographic and Baseline Characteristics**

The number and percentage of subjects screened, randomized/allocated, the primary reasons for screening failure, and the primary reason for discontinuation will be displayed. Demographic variables, baseline characteristics, primary and secondary diagnoses, and prior and concomitant therapies will be summarized.

#### **8.6.3.2 Pharmacokinetics and Pharmacodynamics Modeling Analysis**

Serum concentrations of MK-4280 in each arm, serum concentrations of pembrolizumab in each arm, and plasma concentrations of lenvatinib in Arm 6 will be summarized by planned visit and time for each dose separately. Pharmacokinetic parameters will be summarized by dose. Pharmacokinetic data from subjects from China (Cohort F, Arm 5) will be summarized separately to characterize the PK in this group. Descriptive statistics will be provided for each dose with at least 3 subjects; for other doses, the results will be listed. These analyses will be done on an ongoing basis throughout the study and at the end of the study.

The data from the study will be used to quantitatively explore the relationships among pharmacokinetics, target engagement, exploratory biomarkers, and tumor response measurements.

### **8.6.4 Statistical Methods for Biocomparability Analyses**

To compare the pharmacokinetics between MK-4280A and that of its individual components administered sequentially, pharmacokinetic data from Cohort A, Arm 5 (MK-4280A) and Arm 2C (CRC subjects receiving MK-4280 and pembrolizumab sequentially at the equivalent dose of Arm 5) will be used.

Individual MK-4280  $AUC_{0-21\text{days}}$  and  $C_{\max}$  values from Cycle 1 will be natural log-transformed and analyzed separately in ANCOVA models with effects for treatment, body weight and baseline sLAG-3. Additional covariates deemed significant during PK analysis may also be considered. A 90% CI for the difference in treatment means on the log scale will be calculated using the mean square error from the model and referencing a t-distribution for each endpoint. These confidence limits will be exponentiated to obtain the 90% CI for the ratio of geometric means (MK-4280 from MK-4280A / MK-4280 administered sequentially with pembrolizumab) for MK-4280  $AUC_{0-21\text{days}}$  and  $C_{\max}$ . Pembrolizumab  $AUC_{0-21\text{days}}$  and  $C_{\max}$  from Cycle 1 will be analyzed in a similar fashion. Additional PK parameters such as  $AUC_{0-\infty}$  and soluble LAG-3 exposure parameters ( $AUC_{0-21\text{days}}$ ) from Cycle 1 may also be analyzed in a similar manner.

## 8.7 Interim Analyses

In this study there will be no hypothesis testing. Safety data will be examined on a continuous basis to allow for dose-escalation and dose-confirmation decisions.

In Part B, Arm 2A of the study, an interim analysis will be performed for the CRC and PD-1-treatment-naïve HNSCC cohorts receiving MK-4280 in combination with pembrolizumab. For these tumor cohorts, after 10 subjects have been enrolled and have at least 1 post-baseline scan assessment, the ORR will be evaluated. If an individual cohort experiences an ORR of 20% or greater (ie, at least 2 of 10 subjects), this cohort will be expanded to enroll a maximum of 30 (PD-1-treatment-naïve HNSCC) or 90 (CRC) additional subjects, for a maximum of 40 or 100 subjects in the particular cohort. Enrollment to these cohorts will not be paused in the time period between when 10 subjects have been enrolled and when the interim analysis is performed. If fewer than 2 of 10 subjects experience an objective response in a given cohort, the totality of data will be evaluated to decide whether or not to continue enrollment in that cohort. The operating characteristics of the interim analysis rule are provided in [Table 10](#).

Table 10 Operating Characteristics of Interim Analysis Rule for Each Tumor Type

True ORR	Probability of $\leq 1$ of 10 Subjects Respond
10%	0.74
15%	0.54
20%	0.38
25%	0.24
30%	0.15
35%	0.09
40%	0.05
45%	0.02
50%	0.01

To aid in internal decision making, an interim analysis of efficacy may be performed comparing the 2 doses of MK-4280 in combination with pembrolizumab (Part B, Arm 2A, 2B) administered in the gastric cancer cohort after approximately 25 subjects per dose have been enrolled and have at least 1 post-baseline scan.

Additionally, if antitumor activity is observed in this cohort ( $\geq 8$  of 40 subjects with an objective response, irrespective of dose) an additional 20 subjects with gastric cancer will be enrolled to receive MK-4280 monotherapy at the RP2D. The operating characteristics of the interim analysis rule are provided in [Table 11](#). If this predetermined ORR is not observed, the Sponsor will evaluate all available data before determining whether to enroll these additional subjects or not.

Table 11 Operating Characteristics of Interim Analysis Rule for Determining Conduct of Gastric Cancer Monotherapy Cohort

True ORR for the Combination	Probability Gastric Cancer Monotherapy Cohort Conducted ( $\geq 8$ of 40 Combination Subjects Respond)
10%	0.04
15%	0.24
20%	0.56
25%	0.82
30%	0.94

## 8.8 Multiplicity

There will be no multiplicity control in this study.

## 8.9 Sample Size and Power Calculations

### 8.9.1 Dose Escalation and Dose Confirmation

The primary purpose of the dose-escalation and dose-confirmation parts of the trial is to investigate the safety and tolerability of MK-4280 monotherapy, MK-4280 in combination with pembrolizumab, and MK-4280 in combination with pembrolizumab and either mFOLFOX7, FOLFIRI or lenvatinib in adult subjects with advanced solid tumors (Part A and first 14 subjects in the PD-1-treatment-naïve HNSCC and CRC cohorts in Part B Arm 2A, and Arm 3, Arm 4 and Arm 6 in Part B) and to establish RP2Ds for MK-4280 in combination with pembrolizumab and in combination with pembrolizumab and either mFOLFOX7, FOLFIRI or lenvatinib.

The final number of subjects enrolled in the dose-escalation and dose-confirmation parts of the study will depend on the empirical safety (DLT) observations, in particular, at what dose the 3+3 design is triggered and what dose is identified as the preliminary RP2D. Sample sizes for a few possible scenarios as well as the estimated time required to enroll all subjects and the time required to determine the preliminary RP2D are provided below. The time required to estimate the preliminary RP2D is the time from the first subject's first dose to the end of the 3-week observation period following the first dose of the last subject enrolled in the dose confirmation part. The study duration is derived as the time from the first subject's first dose to the end of 2-year treatment period following the enrollment of the last Part B subject.

Scenario 1. No DLTs during Part A. For MK-4280, in a scenario where no DLTs are encountered during the dose escalation and dose confirmation parts so that Part A continues to the highest dose in [Table 3](#) for both arms, the sample size to determine the preliminary RP2D is 44 subjects (15 in each of the 2 arms of Part A and the first 14 subjects enrolled in Part B Arm 2A who are dosed via the TPI design).

It will take a minimum of 21 weeks to enroll and observe for DLTs in MK-4280 monotherapy and combination subjects in Part A. Total follow-up for the Part A, Arm 2 subjects treated with pembrolizumab would be 104 weeks plus an additional 90 days to observe subjects with SAEs. The duration for Part A, then, is approximately 125 weeks or slightly greater than 2 ½ years.

Part B includes up to a total of 516 subjects. The first 14 subjects in the PD-1-treatment-naïve HNSCC and CRC cohorts enrolled to Part B Arm 2A will be used to further refine the MK-4280 plus pembrolizumab RP2D through the TPI design. The first 14 subjects in each of Arm 3, Arm 4 and Arm 6 from Part B will be used to refine the MK-4280 plus pembrolizumab plus either mFOLFOX7, FOLFIRI or lenvatinib RP2D through the TPI design. It will take approximately 20 months to enroll all subjects for Part B.

Scenario 2: Flat DLT dose-response. Suppose dose escalation in Part A, Arm 1 and Arm 2, continues to the highest dose with flat dose-response so that all 5 doses (including the top one) are given to 6 subjects each. Also suppose that the top dose is confirmed as the preliminary RP2D dose without de-escalation in Part B. Thus, the sample size to determine the preliminary RP2D for MK-4280 plus pembrolizumab is 74 subjects (30 in each of Arm 1 and Arm 2 in Part A and the first 14 subjects enrolled in Part B Arm 2A who are dosed via the TPI design, i.e.,  $30+30+14=74$ ).

Part B includes up to a total of 516 subjects. The first 14 subjects in the PD-1-treatment-naïve HNSCC and CRC cohorts enrolled to Part B Arm 2A will be used to further refine the MK-4280 plus pembrolizumab RP2D through the TPI design. The first 14 subjects in each of Arm 3, Arm 4 and Arm 6 from Part B will be used to refine the MK-4280 plus pembrolizumab plus either mFOLFOX7, FOLFIRI or lenvatinib RP2D through the TPI design. It will take approximately 20 months to enroll all subjects for Part B.

Any dose de-escalations and/or re-escalations in Part B will increase the sample size in these examples.

### **8.9.2 Precision of the DLT Rate at Preliminary RP2D**

Since the TPI approach will be used during the dose confirmation part of the study (Part B Arm 2A), the estimated DLT rate, and its 80% Bayesian Credibility Interval will be calculated from the posterior distribution of the DLT rate at the preliminary RP2D using the model specified in the TPI approach. If 40 subjects are finally dosed at the MK-4280 plus pembrolizumab RP2D during the efficacy expansion for a given tumor type, the estimated DLT rate and its 80% credibility interval should be similar to one of the rows in [Table 12](#). This table also applies for the N=40 subjects dosed at the RP2D of MK-4280 plus pembrolizumab plus lenvatinib (Arm 6). [Table 13](#) presents similar calculations for N=20 subjects dosed at the RP2D for MK-4280 plus pembrolizumab plus either mFOLFOX7 or FOLFIRI.

Table 12 Precision of the Estimated DLT Rates at MK-4280 Plus Pembrolizumab RP2D

Number of Subjects Dosed at RP2D	Number of DLT Events	Estimated DLT Rate	Lower Bound of 80% credibility interval	Upper Bound of 80% credibility interval
40	4	0.10	0.061	0.186
40	6	0.15	0.098	0.243
40	8	0.20	0.137	0.298
40	10	0.25	0.178	0.351
40	12	0.30	0.221	0.402
40	14	0.35	0.264	0.453
Assume non-informative prior distribution of DLT.				

Table 13 Precision of the Estimated DLT Rates at MK-4280 Plus Pembrolizumab Plus Either mFOLFOX7 or FOLFIRI RP2D

Number of Subjects Dosed at RP2D	Number of DLT Events	Estimated DLT Rate	Lower Bound of 80% credibility interval	Upper Bound of 80% credibility interval
20	2	0.10	0.054	0.237
20	3	0.15	0.087	0.295
20	4	0.20	0.123	0.350
20	5	0.25	0.160	0.402
20	6	0.30	0.200	0.453
20	7	0.35	0.240	0.502
Assume non-informative prior distribution of DLT.				

### 8.9.3 Efficacy Expansion

**Table 14**, **Table 15** and **Table 16** show the ORR estimate and the 95% CI (Clopper-Pearson interval) for various sample sizes among the Part B expansion cohorts or additions to cohorts under protocol amendments.

Table 14 Estimate and 95% CI of ORR (N=40)

Number of Responses (PR/CR)	Observed ORR	95% CI of ORR
3	7.5%	(1.6%, 20.4%)
4	10.0%	(2.8%, 23.7%)
5	12.5%	(4.2%, 26.8%)
6	15.0%	(5.7%, 29.8%)
7	17.5%	(7.3%, 32.8%)
8	20.0%	(9.1%, 35.6%)
9	22.5%	(10.8%, 38.5%)
10	25.0%	(12.7%, 41.2%)
11	27.5%	(14.6%, 43.9%)
12	30.0%	(16.6%, 46.5%)
13	32.5%	(18.6%, 49.1%)
14	35.0%	(20.6%, 51.7%)

Number of Responses (PR/CR)	Observed ORR	95% CI of ORR
15	37.5%	(22.7%, 54.2%)
16	40.0%	(24.9%, 56.7%)

Table 15 Estimate and 95% CI of ORR (N=60)

Number of Responses (PR/CR)	Observed ORR	95% CI of ORR
5	8.3%	(2.8%, 18.4%)
6	10.0%	(3.8%, 20.5%)
7	11.7%	(4.8%, 22.6%)
8	13.3%	(5.9%, 24.6%)
9	15.0%	(7.1%, 26.6%)
10	16.7%	(8.3%, 28.5%)

Table 16 Estimate and 95% CI of ORR (N=100)

Number of Responses (PR/CR)	Observed ORR	95% CI of ORR
8	8.0%	(3.5%, 15.2%)
9	9.0%	(4.2%, 16.4%)
10	10.0%	(4.9%, 17.6%)
11	11.0%	(5.6%, 18.8%)
12	12.0%	(6.4%, 20.0%)
13	13.0%	(7.1%, 21.2%)
14	14.0%	(7.9%, 22.4%)
15	15.0%	(8.6%, 23.5%)
16	16.0%	(9.4%, 24.7%)

Though no hypothesis testing will be performed, with 40 subjects per dose level in the gastric cancer cohort, the study has 80% power to detect a ~30% difference in ORR (for example, 55% versus 25%) at alpha=5% (1-sided) between 2 dose levels.

In the Part B MK-4280 monotherapy arms (Arm 1), 20 subjects will be enrolled in each cohort (CRC and gastric, if conducted). If the true ORR is either 5% or 10% for a given cancer type, then the chance of observing at least 1 responder among the 20 subjects will be 64% or 88%, respectively. For each cohort, if there are 0 responses, then there is 88% power to rule out a true ORR >10%.

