### 5.2.3.3 Dose Confirmation – Arm 2A

The objective of dose confirmation in Part B is to refine the estimate of tolerability of the MK-4280 preliminary RP2D (when delivered in combination with pembrolizumab) based on a TPI design [1] with a target toxicity rate less than or equal to 30%, utilizing the first 14 subjects enrolled in this part in Cohort A, Cohort C, and Cohort D. Dose confirmation involves the expansion of at least 1 dose level studied in the dose-escalation stage of the study. After dosing of the first 14 subjects in Part B, dosing will continue as planned.

The 200 mg dose of pembrolizumab will not be adjusted.

Table 4 Dose Confirmation Rules

Number of Toxicities	Number of Subjects Treated at Current Dose										
	4	5	6	7	8	9	10	11	12	13	14
0	S	E	E	E	E	E	E	E	E	E	E
1	S	S	S	S	S	E	E	E	E	E	E
2	D	S	S	S	S	S	S	S	S	S	S
3	DU	D	D	S	S	S	S	S	S	S	S
4	DU	DU	DU	D	D	D	S	S	S	S	S
5		DU	DU	DU	DU	DU	D	D	S	S	S
6			DU	DU	DU	DU	DU	DU	D	D	D
7				DU	D						
8					DU						
9						DU	DU	DU	DU	DU	DU
10							DU	DU	DU	DU	DU
11								DU	DU	DU	DU
12									DU	DU	DU
13										DU	DU
14											DU

E = Escalate to the next higher dose.  
S = Stay at the current dose.  
D = De-escalate to the next lower dose.  
DU = The current dose is unacceptably toxic.  
Target toxicity rate = 30%.  
Noninformative prior is used: a=1; b=1;  
k1=1; k2=1.5; pow=1 per [1].

Subjects may be enrolled continuously (ie, without waiting for Cycle 1 completion of subjects who have received the first dose) unless a DLT is observed at the particular dose. Once a DLT is observed, the number of subjects who are enrolled at that dose but are not yet fully evaluable for DLT assessment may not exceed the number of remaining subjects who are at risk of developing a DLT before the dose would be considered unacceptably toxic (denoted as DU in Table 4). For example, if 3 of 7 subjects have experienced a DLT at a given dose level, no more than an additional 2 subjects should be enrolled at this dose level until additional DLT data are available. This is because this dose level would be considered unacceptably toxic if all 2 of the additional subjects experience a DLT (ie, 5 of 9 subjects with DLT in Table 4). To find out how many more subjects can be enrolled, one can count

steps in diagonal direction (down and to the right) from the cell (7 subjects, 3 toxicities) to the first cell marked DU.

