### **8.6.1 Statistical Methods for Safety Analyses**

Safety and tolerability will be assessed by clinical review of all relevant parameters including AEs, SAEs, laboratory tests, vital signs, ECG measurements, and physical examinations.

Dose limiting toxicities will be listed, and DLTs and AEs will be summarized as counts and frequencies for each MK-4280 dose level administered as monotherapy, in combination with pembrolizumab, or in combination with pembrolizumab and either mFOLFOX7, FOLFIRI or lenvatinib that had at least 3 subjects treated and listed for other dose levels. The estimate of the DLT rate among subjects treated with the preliminary RP2D and the 80% Bayesian credible interval based on a prior distribution of Beta (1,1) for the estimate will be provided.

Laboratory assessments, vital signs, and other safety endpoints will be summarized as appropriate.

In addition, the broad clinical and laboratory AE categories consisting of the percentage of subjects with any AE, a drug-related AE, an SAE, an AE that is both drug-related and serious, and who discontinued due to an AE will be summarized for dose levels with at least 3 subjects treated and listed for other doses.

Data from subjects who experienced disease progression in the Part B monotherapy arm and crossed over into the combination arm will be presented separately.

Data from subjects in Arm 3, Arm 4 and Arm 6 will be summarized separately.

The difference and 95% CI for the rates of infusion related reactions and immune related AEs between MK-4280 administered as a co-formulated product with pembrolizumab (MK-4280A, Arm 5) and MK-4280 and pembrolizumab administered sequentially (Arm 2C, equivalent dose to Arm 5) will be calculated.

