### **8.6.2 Statistical Methods for Efficacy Analyses**

Clinical responses will be listed for subjects in Part A for both the MK-4280 monotherapy arm and the MK-4280 in combination with pembrolizumab arm by dose level.

For the secondary endpoint of ORR, the point estimate and 95% CI will be evaluated separately in Part B subjects treated with MK-4280 monotherapy, in combination with pembrolizumab (separately for co-formulated product or following sequential administration), and in combination with pembrolizumab and either mFOLFOX7, FOLFIRI or lenvatinib at the RP2D for each tumor cohort separately, using an exact method based on binomial distribution (Clopper-Pearson interval).

A comparison will be conducted for ORR between the 2 doses of MK-4280 in combination with pembrolizumab administered in the gastric cancer cohort. Miettinen and Nurminen's

method will be used to estimate the treatment difference between the 2 doses and its 95% CI. Other exploratory endpoints may also be compared between doses (eg, DOR, PFS). Data from subjects who experienced disease progression in the Part B monotherapy gastric arm and crossed over into the combination arm will be summarized separately and will not be included in the dose comparison analysis.

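### Section 8.9.3 labels 88% as power to rule out an ORR above 10% after 0 of 20 responses; it is a one-sided confidence level, and the planned 95% interval would reach 16.8%

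*Combined protocol and SAP*

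**What the plan says.** Section 8.9.3 plans Arm 1 of Part B so that "20 subjects will be enrolled in each cohort (CRC and gastric, if conducted"). It gives two operating characteristics. First, for a true ORR of 5% or 10%, "the chance of observing at least 1 responder among the 20 subjects will be 64% or 88%, respectively". Second, "For each cohort, if there are 0 responses, then there is 88% power to rule out a true ORR >10" percent.

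Section 8.6.2 commits to a point estimate and 95% CI for ORR in the monotherapy subjects, for each tumor cohort separately, "using an exact method based on binomial distribution (Clopper-Pearson interval"). Section 8.7 states: "In this study there will be no hypothesis testing". Tables 14 to 16 illustrate ORR intervals for N = 40, 60 and 100. There is none for N = 20, so the disputed sentence is the only statement of what 0 of 20 would show.

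On the side point, Section 8.6.1 specifies for the DLT rate an "80% Bayesian credible interval based on a prior distribution of Beta (1,1"). The notes to Table 4 in Section 5.2.3.3 agree: "Noninformative prior is used: a=1; b=1". Section 8.9.2 describes Table 13 (N = 20) as the same kind of calculation as Table 12 (N = 40).

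**The concern.** Power is a probability fixed before the data are seen: the chance of reaching a stated conclusion under an assumed true value. The sentence conditions instead on a result already observed, 0 of 20. It gives no alternative ORR under which the conclusion would be reached and no significance level.

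The practical issue is how an empty monotherapy cohort would be read. These cohorts exist to look for single-agent activity, and zero responses is a plausible outcome: its probability is 12% if the true ORR is 10% and 36% if it is 5%. A reader of Section 8.9.3 could take 0 of 20 as ruling out an ORR above 10% with good power. The interval reported under Section 8.6.2 would run well past 10%.

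**Working it through.** **Inputs.** n = 20 per monotherapy cohort, and true ORR of 5% and 10% (Section 8.9.3). Two-sided 95% Clopper-Pearson interval (Section 8.6.2). Beta(1,1) prior and 80% credible interval for DLT rates (Sections 8.6.1 and 5.2.3.3).

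**Step 1: reproduce the plan's figures.** P(at least 1 response) = 1 − (1 − p)^20.
- p = 0.05: 1 − 0.95^20 = 0.6415, printed as 64%.
- p = 0.10: 1 − 0.9^20 = 0.8784, printed as 88%.

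Both are correct as chances of seeing at least one responder.

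**Step 2: what 88% means after 0 of 20.** P(0 of 20 | ORR 10%) = 0.9^20 = 0.1216. The exact upper bound for 0 of 20 at one-sided confidence 1 − a solves (1 − p)^20 = a. Setting p = 0.10 gives a = 0.1216, so 10% is the one-sided 87.8% upper confidence bound. That is a confidence level.

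**Step 3: what power would look like.** If the rule is to conclude that the ORR is at most 10% when 0 of 20 respond, its power is the chance of 0 of 20 under some lower true ORR:
- ORR 1%: 0.99^20 = 81.8%
- ORR 2%: 0.98^20 = 66.8%
- ORR 5%: 0.95^20 = 35.8%

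The plan names no such ORR.

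**Step 4: the planned interval.**
- Two-sided 95% Clopper-Pearson upper limit for 0 of 20: 1 − 0.025^(1/20) = 0.1684, or 16.8%.
- One-sided 95% bound: 1 − 0.05^(1/20) = 0.1391, or 13.9%.

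Neither excludes 10%. Zero is the smallest possible count, so no outcome at N = 20 gives a planned interval lying below 10%. For zero responses to exclude 10%, n must be 29 at one-sided 95% (0.9^29 = 0.047; 0.9^28 = 0.052) or 36 for the two-sided 95% interval (0.9^36 = 0.0225; 0.9^35 = 0.02503).

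The same Clopper-Pearson calculation reproduces the printed rows checked in Tables 14 to 16 (3/40, 8/40, 5/60, 8/100).

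**Side check: Table 13.** With a Beta(1,1) prior and x DLTs in 20, the bounds are the 10th and 90th percentiles of Beta(1 + x, 21 − x).

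| DLTs in 20 | Printed | Beta(1,1) |
|---|---|---|
| 2 | 0.054, 0.237 | 0.054, 0.234 |
| 3 | 0.087, 0.295 | 0.086, 0.291 |
| 4 | 0.123, 0.350 | 0.121, 0.345 |
| 5 | 0.160, 0.402 | 0.158, 0.397 |
| 6 | 0.200, 0.453 | 0.196, 0.448 |
| 7 | 0.240, 0.502 | 0.236, 0.497 |

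Eleven of the 12 bounds differ. The largest gap is 0.0054 before rounding (upper bound for 7 of 20). The printed intervals still hold 0.800 to 0.804 of the Beta(1,1) posterior. In Table 12, Beta(1 + x, 41 − x) reproduces all 12 bounds, so the two tables were not produced in the same way. The documents do not show why.

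**The case against.** The strongest reply is that nothing is miscalculated. Both 64% and 88% are right, and for an informal screen that looks for at least one responder, 88% is the chance of passing it when the true ORR is 10%. The sentence also states its own level: it does not claim exclusion at 95%. A one-sided 88% bound at 10% and a two-sided 95% limit at 16.8% are both correct descriptions of 0 of 20, and the 95% interval will be reported in any case. Section 8.9.3 also uses power informally for the gastric dose comparison, with a caveat that no hypothesis is tested.

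Much of this stands. The defect is one of labelling and interpretation, and the 88% needs renaming, not reducing. It does not rescue the sentence. Detecting at least one responder is a different event from ruling out 10% after none, and attaching 88% power to the second is wrong. The gastric statement gives an alpha and two ORRs, while the monotherapy statement gives no alpha, no alternative and no caveat.

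It is also fair to say that Table 13 is a separate matter: a different section, endpoint and set of arms, in a table offered as illustration, with discrepancies too small to change any reading. It is reported here only as a minor correction.

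**Conclusion.** The concern holds. The 88% in the disputed sentence is one-sided confidence (87.8%) that the ORR is at most 10% once 0 of 20 has been seen. It is not power. Under the plan's own 95% method the upper limit for that result is 16.8%, so the planned interval cannot exclude 10% at N = 20. Choosing a one-sided 95% bound does not change the conclusion (13.9%).

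This assumes that all 20 subjects are in the full analysis set; with fewer, the limit rises. The importance is low. ORR is a secondary, estimation-only endpoint, no decision rule uses the sentence, and no dose decision uses Table 13. What is at stake is the interpretation of a null monotherapy cohort.

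**What to change.** Replace the sentence in Section 8.9.3 with wording such as:

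> If 0 of 20 subjects respond, the upper limit of the 95% Clopper-Pearson interval is 16.8%; a true ORR above 10% is excluded only at about 88% one-sided confidence.

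The preceding sentence on the chance of at least one responder can stay as it is.

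As a separate minor correction, recompute Table 13 from the Beta(1,1) posterior, using the bounds in the right-hand column above, or state the prior actually used.

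The cost is one sentence and one illustrative table. Sample size, analysis method and decision rules do not change.
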